4.3. Justification for Dose

4.3.1. Predicted Human Pharmacokinetics

The pharmacokinetic profile for VH3739937 in humans was predicted using allometric scaling across all species (mouse, rat, dog, and monkey), and was combined with Css-MRT modeling to obtain the predicted human PK profile [GlaxoSmithKline Document Number [2020N427033_00](#)]. Using this method, the intravenous (IV) plasma clearance in humans for VH3739937 is projected to be low (0.12 mL/min/kg) and the intravenous volume of distribution was predicted to be 0.25 L/kg. The elimination half-life was

anticipated to be around 24 hours, leading to an approximate 2-fold anticipated accumulation with once daily dosing. The mean oral bioavailability in animals was approximately 12% (based on simultaneous fitting of the IV and oral animal data using compartmental modeling) and assumed for exposure projections in humans.

4.3.2. Predicted Human Effective Dose

Trough concentrations (C_t) are typically the PK parameter of interest for efficacy for other antiretroviral classes such as protease inhibitors and integrase inhibitors. The target C_t for VH3739937 was established using the average of 3-times the protein binding-adjusted EC₉₀ (3xPBA-EC₉₀) for a small library of 6 Gag/Pr genotyped viruses less sensitive to a precursor maturation inhibitor GSK3640254. These viruses exhibited an average 3xPBA-EC₉₀ of 312 nM (0.258 μ g/mL). A similar 3xPBA-EC₉₀ value was observed towards Δ 370 virus (309 nM). The predicted dose that achieves a C_t at steady-state \geq target concentration in \sim 95% of the simulated subjects will be selected as the minimal effective dose.

Prior to study initiation, the rationale for estimation of the minimally effective dose and associated PK parameters was as follows:

The potential minimal effective dose for VH3739937 was estimated using the predicted human PK profile, assuming 50% between subject variability (IIV) on CL, V₂ and K_a, the same parameters for which moderate to high IIV was estimated in a preliminary population PK model for GSK3640254, based on data from a FTIH study profile [GlaxoSmithKline Document Number [2020N427033_00](#)]. This led to the prediction of a likely minimally effective once daily dose of approximately 80 mg. At this dose, the mean repeat-dose C_{max} is predicted to be approximately 0.94 μ g/mL, mean C_t is predicted to be approximately 0.68 μ g/mL and mean AUC is predicted to be approximately 20.1 μ g*h/mL ([Table 10](#)). The anticipated steady-state mean AUC is 1.27-fold lower than the no observed adverse effect level (NOAEL) in the rat (25.5 μ g*h/mL), 4.79-fold lower than the lowest observed adverse effect level (LOAEL) in the rat (96.2 μ g*h/mL), and 2.58-fold lower than the LOAEL in the dog (51.9 μ g*h/mL).

However, during the course of study 212548 conduct, modelling and simulation of PK data from SAD treatment Periods 10 mg, 30 mg, 80 mg, 160 mg, 320 mg and 640 mg have led to the revision of the estimation of the predicted minimally effective dose and associated PK parameters. More detailed information may be found in the IB Supplement [GlaxoSmithKline Document Number [2021 RPS_CLIN_004025](#)].

4.3.3. Part 1 (SAD) Starting Dose and Dose Escalation

The starting oral dose of VH3739937 in the SAD will be 10 mg. Assuming a 10-fold safety factor and a body weight of 70 kg, this starting dose is lower than that calculated based on the NOAEL in rat of 10 mg/kg/day (maximum recommended starting dose [MRS_D] = 11.3 mg) and the LOAEL in dog of 3 mg/kg (MRS_D = 11.7 mg), in the absence of a NOAEL in dog [[FDA/CDER](#), 2005]. Although a NOAEL was not established in the 4-week dog study due to the presence of gastric toxicity at all doses, the gastric findings at 3 mg/kg/day (LOAEL) were minimal in severity and reversible.

Based on the predicted human PK, a 10 mg dose would provide a mean AUC(0-inf) of 2.58 $\mu\text{g}^*\text{h}/\text{mL}$ and a mean Cmax of 0.0454 $\mu\text{g}/\text{mL}$. This predicted AUC(0-inf) is ~10-fold lower than that observed in the rat at the NOAEL (25.5 $\mu\text{g}^*\text{h}/\text{mL}$), 20.1-fold lower than that observed in the dog at the LOAEL (51.9 $\mu\text{g}^*\text{h}/\text{mL}$), and 37.3-fold lower than that observed in the rat LOAEL (96.2 $\mu\text{g}^*\text{h}/\text{mL}$).

Dose escalations in Part 1 (SAD) will be governed in real-time by safety and PK stopping criteria (see Section 7.1.4. and Section 7.1.5). Based on the assumptions described above, the top dose anticipated in Part 1 was a single dose of 640 mg. However, following review and evaluation of emerging available PK and safety data, a higher SAD dose of 800 mg was selected for evaluation in Cohort 1, Period 4. Observed exposures were lower than that projected and review of preliminary safety data from the SAD 10mg through to 640mg dose and the MAD 25mg dose, supported escalation to the 800mg dose. These preliminary PK and safety data are summarised in the IB Supplement [GlaxoSmithKline Document Number 2021 [RPS_CLIN_004025](#)]. The predicted median Cmax for 800 mg dose was 1.60 $\mu\text{g}/\text{mL}$. This higher 800mg dose will be in accordance with SAD PK stopping criteria. Based on the data collected from the observed doses so far in the study, the probability of any SAD participant having a Cmax $> 21 \mu\text{g}/\text{mL}$ is extremely low.

4.3.4. Part 2 (MAD) Starting Dose and Dose Escalation

The initial dose in the MAD (Cohort 3) was approximately equal to the likely minimally effective dose, re-estimated at 25 mg based on the clinical PK data following oral administration of the suspension formulation collected in the early doses of Part 1. Dose escalation in the MAD will not exceed 2-fold between daily dosing cohorts 4 and 5 and will be governed by both safety and MAD PK stopping criteria (see Section 7.1.4 and Section 7.1.5). Based on emerging PK data in Part 1, the once weekly (QW) dosing Cohort 6 will be dosed at 500 mg. Given different assumptions for the between participant AUC variability (%CVb) and the current human PK prediction, the probability of any participant AUC(0- τ) in the MAD above 96.2 $\mu\text{g}/\text{mL}$, the LOAEL exposure in rat, are illustrated in [Table 8](#). Similarly, the probability of any participant AUC(0-24) which cover the maximum exposure in the MAD Cohort 6 above 96.2 $\mu\text{g}/\text{mL}$ is illustrated in [Table 9](#).

Table 8 Probability of any MAD participant (AUC(0- τ) $> 96.2 \mu\text{g}^*\text{h}/\text{mL}$) for potential QD doses

AUC variability	Potential VH3739937 QD MAD Doses		
	25 mg	50 mg	100 mg
25	0	0	<0.001
35	0	0	0.003
50	0	<0.001	0.028

Note: 1, %CVb: between-participant coefficient of variation

Table 9 Probability of any MAD participant (AUC(0- τ) >96.2 $\mu\text{g}^*\text{h}/\text{mL}$ and (Cmax >21 $\mu\text{g}/\text{mL}$) for 500 mg QW dose

AUC variability (%CVb ¹)	Cmax Variability (%CVb ¹)	Any Participant (AUC >96.2 $\mu\text{g}^*\text{h}/\text{mL}$ or Cmax >21 $\mu\text{g}/\text{mL}$)
25	25	0

Note: 1, %CVb: between-participant coefficient of variation

Given the results in the tables above, it is unlikely that any subject exceeds the safety thresholds in the QD or QW MAD portions of the study.

4.3.5. Part 3 RBA Dose Selection

The relative bioavailability of a 100 mg tablet formulation will be assessed in Part 3, using the PiB formulation as a reference. A 100 mg unit tablet dose was chosen as a reasonable representative dose for this assessment, given available PiB pharmacokinetic data and projected clinical doses (25 mg QD or 500 mg QW).

Although no definitive preclinical data on solid dose bioavailability is available, it is unlikely that moving to a tablet will result in significantly higher exposure (as Cmax or AUC) relative to a 100 mg PiB dose. Given doses of up to 640 mg PIB have been safely administered in Part 1, there is no perceived safety risk.

4.3.6. Dose Escalation Committee (DEC)

This study will utilize a dose escalation committee made up of at least the following: Sponsor and Site staff (including safety physicians and clinicians, PI, Sub-Investigator, Medical Monitor, clinical pharmacokineticist/pharmacologist, data manager, pharmacovigilance, and statistician) and/or their delegates. The committee will evaluate data including but not limited to: AEs, vital signs, laboratory findings, ECG parameters, and PK data. The DEC will meet when data are available from a minimum of 4 active treated participants through Day 16 assessments in Part 1, and from a minimum of 5 active treated participants through Day 29 assessments in Part 2 Cohorts 3 and 4, and similarly through Day 33 assessments in Cohort 5. A dose escalation plan will document the structure and function of the DEC. This plan is included in the Dose Escalation Charter which will also specify the safety and PK requirements for the DEC prior to making a dose escalation decision. The blinding of personnel is discussed in Section 6.4.

4.3.7. Anticipated Exposure and Safety Cover for a Range of Potential Doses

Projected steady-state exposures of GSK3739937 from potential doses in Part 2 are compared to target efficacious concentrations and preclinical toxicity exposures in Table 10. Projected steady-state PK for a range of potential QD (50-100 mg) or QW (500 mg) doses following fed administration and comparison to efficacy target and preclinical exposure in Table 11. Predicted human exposure following multiple doses can be compared to the NOAEL and LOAEL in rats, the Cmax from the dog CV study and to LOAEL in dogs. Findings in both species were GI related, limited and reversible (see

Section 2.3.1 and the Clinical Investor Brochure [GlaxoSmithKline Document Number 2019N421306_00] for further details).

Importantly, the doses listed here are intended to demonstrate general concepts relating to factors of escalation. The specific doses in the SAD and MAD portions are subject to change based upon emerging clinical and PK data gathered in this study. As described above, dose escalations will be governed in real-time by safety and PK. A dose which has met formal clinical, QT, and PK stopping criteria (see Section 7) will not be repeated in the SAD or MAD.

Table 10 Projected steady-state PK for a range of potential QD doses following fed administration and comparison to efficacy target and preclinical exposure

Parameter	10 mg	30 mg	80 mg	160 mg	320 mg
C_τ, µg/mL					
Mean	0.085	0.255	0.68	1.36	2.72
Lower bound of 90% CI	0.036	0.107	0.28	0.57	1.14
C_τ/Ctarget (0.258 µg/mL)					
Lower bound of 90% CI	0.140	0.421	1.12	2.24	4.49
Cmax Day 14, µg/mL					
Mean	0.117	0.352	0.939	1.88	3.76
Upper bound of 80% CI ^a	0.207	0.620	1.65	3.31	6.61
Cmax Cover with^b					
Dog 1-month GLP study (39.8 µg/mL) ^c	729	242	90.8	45.4	22.7
Dog CV study (9.82 µg/mL) ^d	180	59.8	22.4	11.2	5.60
Mean AUC, µg*h/mL					
Mean	2.51	7.52	20.1	40.1	80.2
Upper bound of 80% CI ^a	4.63	13.9	37.0	74.1	148
AUC Cover with^b					
Rat NOAEL (25.5 µg*h/mL)	10.16	3.39	1.27	0.636	0.318
Rat LOAEL (96.2 µg/mL)	38.3	12.8	4.79	2.40	1.20
Dog LOAEL (51.9 µg/mL)	20.7	6.90	2.58	1.29	0.647

- a. The upper bound of the 80% CI is presented to capture the likely highest PK values in 6 subjects.
- b. The Cmax and AUC cover were computed as the ratio of Cmax or AUC in animal divided by the mean Cmax or AUC predicted in human.
- c. Equivalent to 85.3 µg/mL in human (based on 85% and 93% protein binding in dog and human, respectively).
- d. Equivalent to 21.0 µg/mL in human (based on 85% and 93% protein binding in dog and human, respectively).

Table 11 Projected steady-state PK for a range of potential QD (50-100 mg) or QW 500 mg doses following fed administration and comparison to efficacy target and preclinical exposure

Parameter	50 mg	100 mg	500 ^e mg
C_τ, µg/mL			
Median	0.905	1.57	0.429
Lower bound of 90% CI	0.557	1.01	0.253
C_τ/Ctarget (0.258 µg/mL)			
Lower bound of 90% CI	2.16	3.91	0.981
Cmax after last dose, µg/mL			
Median	0.968	1.72	1.5
Upper bound of 90% CI ^a	1.53	2.65	2.07
Cmax Cover with^b			
Dog 1-month GLP study (39.8 µg/mL) ^c	88.1	49.6	58.8
Dog CV study (9.82 µg/mL) ^d	21.7	12.2	14.5
Mean AUC, µg*h/mL			
Median	22.7	39.8	31.3
Upper bound of 90% CI ^a	36.1	62.0	45.5
AUC Cover with^b			
Rat NOAEL (25.5 µg*h/mL)	1.12	0.641	0.815
Rat LOAEL (96.2 µg/mL)	4.24	2.42	3.07
Dog LOAEL (51.9 µg/mL)	2.29	1.30	1.66

- a. The upper bound of the 95% PI is presented to capture the likely highest PK values.
- b. The Cmax and AUC cover were computed as the ratio of Cmax or AUC in animal divided by the median Cmax or AUC predicted in human.
- c. Equivalent to 85.3 µg/mL in human (based on 85% and 93% protein binding in dog and human, respectively).
- d. Equivalent to 21.0 µg/mL in human (based on 85% and 93% protein binding in dog and human, respectively).
- e. The weekly dose 500 mg
- f. the maximum 24 hour AUC were calculated from 0-24h after the last dose to match the daily safety limit 96.2 ug*h/mL

4.4. End of Study Definition

A participant is considered to have completed the study if he/she has completed all phases of the study including the last visit and the last scheduled procedure shown in the [SoA](#)

The end of the study is defined as the date of the last visit of the last participant in the study.

5. STUDY POPULATION

Prospective approval of protocol deviations to recruitment and enrolment criteria, also known as protocol waivers or exemptions, is not permitted.

5.1. Inclusion Criteria

Participants are eligible to be included in the study only if all of the following criteria apply:

AGE
1. Participant must be 18 to 55 years of age inclusive, at the time of signing the informed consent.

TYPE OF PARTICIPANT AND DISEASE CHARACTERISTICS
2. Participants who are overtly healthy as determined by the investigator or medically qualified designee based on a medical evaluation including medical history, physical examination, laboratory tests, and cardiac monitoring (history and ECG). 3. Participants who are negative on two consecutive tests for SARs-CoV-2, performed at Screening, on admission and (re-)admission to the Phase I unit, using an approved molecular test (PCR). 4. Participants who are able to understand and comply with protocol requirements and timetables, instructions, and protocol-stated restrictions.

WEIGHT
5. Body weight ≥ 50.0 kg (110 lbs.) for men and ≥ 45.0 kg (99 lbs) for women and body mass index within the range 18.5 to 32.0 kg/m^2 (inclusive).

SEX
6. Male and/or female Male participants: Male participants are eligible to participate if they agree to the following during the intervention period and for at least 5 days, corresponding to time needed to eliminate study intervention(s) (e.g. 5 terminal half-lives) plus an additional 90 days (a spermatogenesis cycle) after the last dose of study intervention: 
• Refrain from donating sperm PLUS either: 
• Be abstinent from heterosexual or homosexual intercourse as their preferred and usual lifestyle (abstinent on a long term and persistent basis) and agree to remain abstinent

OR

- Must agree to use a male condom

AND

And female partner to use an additional highly effective contraceptive method with a failure rate of <1% per year as described in [Appendix 4](#)

OR

And should also be advised of the benefit for a female partner to use a highly effective method of contraception as a condom may break or leak when having sexual intercourse with a woman of childbearing potential who is not currently pregnant

- Agree to use male condom when engaging in any activity that allows for passage of ejaculate to another person.

Female participants:

A female participant is eligible to participate if she is not pregnant or breastfeeding, and is not a woman of childbearing potential (WOCBP) as defined in [Appendix 4](#).

Additional requirements for pregnancy testing during and after study intervention are located in [Appendix 2](#).

The investigator is responsible for review of medical history, menstrual history, and recent sexual activity to decrease the risk for inclusion of a woman with an early undetected pregnancy.

INFORMED CONSENT

7. Capable of giving signed informed consent as described in [Appendix 1](#), which includes compliance with the requirements and restrictions listed in the informed consent form (ICF) and in this protocol.

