In Part 3, the RBA and FE (Cohort 7) will include a randomized, open-label, single dose, 3-period crossover design to compare the RBA of single doses of the GSK3739937 PiB with GSK3739937 Tablet, and to assess the effect of food (fasted or fed (under moderate calorie and fat conditions)) upon the safety, tolerability and PK of the GSK3739937 Tablet ([Figure 2](#)). All doses will be administered immediately following a standardized meal for each dosing period that contains approximately 600 calories with approximately 30% of calories from fat (unless otherwise indicated in Part 3 dosing in fasted condition).

A summary of the overall study design, including doses, sample size, and order, is presented in [Figure 1](#) and [Figure 2](#) below.

Figure 1 Phase 1 Study in Healthy Participants using planned doses of VH3739937 Part 1 and Part 2

[figure not shown]
A=Active; P=Placebo

QD = once daily; QW = once weekly

*= Period 4 may include participants from both Cohorts 1 and 2

Highlighted cohorts and treatment periods denote completed

Figure 2 Phase 1 Study in Healthy Participants using planned doses of VH3739937 Part 3

Note: The doses shown in Figure 1 above are intended to demonstrate general concepts relating to factors of escalation. The modelling and simulation implemented using the data currently available following oral administration of a suspension formulation in the fed state indicated the predicted efficacious dose for the daily dose is 25 mg and the weekly dose is 500 mg. Due to the observed half-life of ~90 h, the anticipated accumulation ratio following repeated daily and weekly doses is ~ 6-fold and 1.3-fold, respectively. Dosing will be conducted in accordance with PK stopping criteria.

In Part 1, dose escalation will be determined by the Dose Escalation Committee (ViiV Healthcare (VH)/GlaxoSmithKline (GSK) study team and the Principal Investigator (PI))

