- Any changes in the timing or addition of time points for any planned study assessments, or changes in the duration and schedule of dosing and the doses to be administered in the SAD and MAD cohorts, as the result of emerging PK data from this study, must be documented and approved by the relevant study team member and then archived in the sponsor and site study files but will not constitute a protocol amendment.

Table 1 Screening and Follow-Up Assessments (Part 1, Part 2, and Part 3)¹

Procedure	Screening (up to 28 days before Day 1)	Follow-Up ² (approx. 28 days post last dose)	Notes
Outpatient Visit	X	X	
Informed Consent	X		
Inclusion/Exclusion Criteria and Demography	X		
Medical/medication/drug/alcohol history	X		
Full Physical Examination	X	X	A Full Physical Exam will include at a minimum, assessments of the Skin, Cardiovascular, Respiratory, Gastrointestinal and Neurological systems
SARS CoV-2 Testing ²	X		An approved molecular test (PCR) will be used. For further detail see Appendix 7 and Section 8.1.3
Columbia Suicide Severity Rating Scale (CSSRS) ²	X		
Height, Weight, Body Mass Index (BMI)	X		
Vital signs	X	X	
12 Lead ECG	X	X	TriPLICATE ECGs will be used to determine participant eligibility at screening
Pregnancy Test	X	X	Follow up test may be obtained up to 37 days post last dose
Urine drug/alcohol/cotinine screen	X		Performed at the standard practice of the site
Hepatitis B surface antigen (HbsAg), Hepatitis C (HCV), Human immunodeficiency virus (HIV) tests ³	X		If test otherwise performed within 3 months prior to first dose of study intervention, testing at screening is not required
Haematology/Chemistry/Urine tests	X	X	Laboratory procedures may be repeated and additional tests may be performed, if needed, at the discretion of the investigator.
Serious Adverse Event (SAE) Review	X	X	All SAEs will be collected from screening visit until the follow up visit
AE Review		X	All AEs will be collected from start of intervention until follow up visit
Concomitant Medication Review	X	X	

¹ In a pandemic situation see [Appendix 7](#)²For early discontinuation that occurs prior to discharge from unit, SARS-CoV-2 testing, CSSRS, and final follow up assessments will be performed. For early discontinuation that occurs post discharge from unit, only final follow up assessments will be performed.³ HIV Ab/Ag 4th generation test (point of care test or laboratory immunoassay)

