To characterize the population pharmacokinetics of VH3739937 and identify important determinants of variability, a population model was conducted as an alternate analysis approach to characterize the pharmacokinetics and the simulation was implemented to predicted the higher single dose and multiple dose cohort PK profile based on the model. The PK of VH3739937 following oral administration was adequately characterized by a linear one-compartment model with first-order absorption and first-order elimination, and with a dose factor and inter-individual variability on CL/F and on the magnitude of proportional residual error. The simulations for higher single dose 640 and 800 mg, multiple daily dose 50 and 100 mg and the multiple weekly dose 500 mg were conducted to predict the PK profile to obtain the Cmax and AUC for safety cover. More detailed information can be found in the Investigator's Brochure Supplement [GlaxoSmithKline Document Number [2021 RPS_CLIN_004025](#)].

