All participants will have a screening visit within 28 days prior to first dose and a follow-up visit approximately 28 days after the last dose. All dosing will be conducted in a hospital based inpatient clinical trial unit. Study participants will be confined to the clinic from Day -2 until discharge. Additional outpatient visits will be required for all study parts. Flexibility of visit scheduling may be required if a pandemic situation applies (see Appendix 7). Otherwise, study assessments will be performed as indicated in the SoA presented in this protocol.

A summary of the overall study design, including proposed doses, sample size, and order, is presented in Figure 3 and Figure 4 below.

Figure 3 Phase 1 Study in Healthy Participants using planned doses of VH3739937 Part 1 and Part 2

A=Active; P=Placebo

QD = once daily; QW = once weekly

*= Period 4 may include participants from both Cohorts 1 and 2

Highlighted cohorts and treatment periods denotes completed

The doses shown in [Figure 3](#) above are intended to demonstrate general concepts relating to factors of escalation. The modelling and simulation implemented using the data currently available following oral administration of a suspension formulation in the fed state indicated the predicted efficacious dose for the daily dose is 25 mg and the weekly dose is 500 mg. Due to the observed half-life of ~90 h, the anticipated accumulation ratio following repeated daily and weekly doses is ~6-fold and 1.3-fold, respectively. Dosing will be conducted in accordance with safety and PK stopping criteria (Section [7.1.4](#)).

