8.2.5. Pregnancy

- Details of all pregnancies in female participants and, if indicated, female partners of male participants will be collected after the start of study intervention and until 5 days [at least 5 terminal half-lives] after last dose of study intervention.
- If a pregnancy is reported, the investigator will inform GSK within 24 hours of learning of the pregnancy and will follow the procedures outlined in [Appendix 4](#).
- Abnormal pregnancy outcomes (e.g., spontaneous abortion, fetal death, stillbirth, congenital anomalies, ectopic pregnancy) are considered SAE.

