
 a. Contraceptive use by men or women should be consistent with local regulations regarding the use of contraceptive methods for those participating in clinical studies. b. Failure rate of <1% per year when used consistently and correctly. Typical use failure rates differ from those when used consistently and correctly. c. Male condoms must be used in addition to hormonal contraception. If locally required, in accordance with Clinical Trial Facilitation Group (CTFG) guidelines, acceptable contraceptive methods are limited to those which inhibit ovulation as the primary mode of action.

Note: Periodic abstinence (calendar, 121ymptom-thermal, post-ovulation methods), withdrawal (coitus interruptus), spermicides only, and lactational amenorrhoea method (LAM) are not acceptable methods of contraception for the study. Male condom and female condom should not be used together (due to risk of failure with friction)

10.4.3. Collection of Pregnancy Information:

Male participants with partners who become pregnant

- Investigator will attempt to collect pregnancy information on any male participant's female partner of a male study participant who becomes pregnant while participating in this study. This applies only to male participants who receive VH3739937
- After obtaining the necessary signed informed consent from the pregnant female partner directly, the investigator will record pregnancy information on the appropriate form and submit it to GSK within 24 hours of learning of the partner's pregnancy.
- The female partner will also be followed to determine the outcome of the pregnancy. Information on the status of the mother and child will be forwarded to GSK.
- Generally, follow-up will be no longer than 6 to 8 weeks following the estimated delivery date. Any termination of the pregnancy will be reported regardless of fetal status (presence or absence of anomalies) or indication for procedure.

Female Participants who become pregnant

- Investigator will collect pregnancy information on any female participant, who becomes pregnant while participating in this study.
- Information will be recorded on the appropriate form and submitted to GSK within 24 hours of learning of a participant's pregnancy.

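### The 5-day elimination period in Protocol 5.1 (criterion 6) and 8.2.5 fits the predicted 24 h half-life; at the observed ~90 h, five half-lives take about 19 days

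*Protocol*

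**What the plan says.** Three places set a duration that bears on reproductive safety after dosing.

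- **Protocol 5.1, criterion 6.** Male participants must follow the contraception and sperm-donation rules after the last dose "for at least 5 days, corresponding to time needed to eliminate study intervention(s) (e.g. 5 terminal half-lives) plus an additional 90 days". The 90 days stand for one spermatogenesis cycle.
- **Protocol 8.2.5.** Pregnancy details, for women in the study and for men's partners where indicated, have this collection window: "will be collected after the start of study intervention and until 5 days [at least 5 terminal half-lives] after last dose of study intervention".
- **Protocol Appendix 4 (10.4.3).** For men, collection covers a "female partner of a male study participant who becomes pregnant while participating in this study". No day count is given. Participation runs to a follow-up "visit approximately 28 days after the last dose" (4.1).

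The half-life behind the day counts appears in two forms. Section 4.3.1 gives the prediction made before the study, "anticipated to be around 24 hours, leading to an approximate 2-fold anticipated accumulation with once daily dosing". Sections 1.1 and 4.1 give the current value: "Due to the observed half-life of ~90 h", daily and weekly accumulation of about 6-fold and 1.3-fold are expected.

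**The concern.** Sections 5.1 and 8.2.5 each state a rule (five terminal half-lives) and a number (5 days). The rule and the number agreed when the half-life was expected to be about 24 h. They no longer agree now that it is reported as ~90 h. The current protocol lengthened other windows to suit the slower elimination: PK sampling runs to 360 h after the dose and the Part 3 washout is 24 days. These two clauses kept the old number.

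Two things are at stake. In criterion 6, the 90-day spermatogenesis cycle is meant to start once the drug has been eliminated. With the elimination allowance too short, part of that cycle is used up while drug is still present. In 8.2.5, the window closes early. Discharge from the unit is 120 h after the last dose in Parts 1 and 2 (SoA), so a 5-day window ends at about the time a man goes home and misses the outpatient weeks. Women of childbearing potential are excluded, so the effect falls mainly on partners of male participants.

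**Working it through.** **Inputs**

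- Predicted half-life: about 24 h (Protocol 4.3.1).
- Observed half-life: ~90 h (Protocol 1.1 and 4.1).
- Elimination rule: five terminal half-lives (5.1 criterion 6; 8.2.5).
- Spermatogenesis cycle: 90 days (5.1 criterion 6).
- Follow-up visit: about 28 days after the last dose (4.1).
- Kinetics: a "linear one-compartment model with first-order absorption and first-order elimination" (2.2.1), so the fraction remaining after time t is 2^(-t / half-life).

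**Reproducing the plan's figure.** Elimination period in days = 5 x half-life / 24. With 24 h this is 5 x 24 / 24 = 5.0 days, and 5 + 90 = 95 days. The stated figures reproduce exactly, but only with the superseded half-life.

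**Checking the 90 h input.** Accumulation at steady state = 1 / (1 - 2^(-tau / half-life)).

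- Daily dosing: 1 / (1 - 2^(-24/90)) = 5.9, against the protocol's ~6.
- Weekly dosing: 1 / (1 - 2^(-168/90)) = 1.38, against 1.3.

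The protocol's own accumulation figures therefore rest on a half-life of about 90 h.

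**Recomputing at 90 h**

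| Quantity | Stated | By the stated rule at 90 h |
|---|---|---|
| Five half-lives | 5 days | 5 x 90 h = 450 h = 18.75 days |
| Male contraception and sperm donation | 5 + 90 = 95 days | 18.75 + 90 = 108.75 days |
| Pregnancy-collection window (8.2.5) | 5 days | 18.75 days |

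The shortfall is 18.75 - 5 = 13.75 days in each case.

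**What the shortfall means**

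- Contraception: 95 x 24 / 90 = 25.3 half-lives, so drug has gone by day 95. The margin after elimination is 95 - 18.75 = 76.25 days, which is 76.25 / 90 = 85% of the intended cycle.
- Pregnancy window at day 5: 120 / 90 = 1.33 half-lives, leaving 2^(-1.33) = 40% of drug. Five half-lives would leave 3.1%.
- Follow-up visit at day 28: 672 / 90 = 7.47 half-lives, leaving 2^(-7.47) = 0.6%.

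**Comparison with windows set elsewhere.** The 24-day Part 3 washout is 24 x 24 / 90 = 6.4 half-lives. The SAP's on-treatment window of last dose plus 22 days (Appendix 4, 13.4) is 22 x 24 / 90 = 5.9 half-lives. Both satisfy a five-half-life rule at 90 h; 5 days does not.

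**Sensitivity.** The half-life is given only approximately. Under an assumed range of 80 to 100 h, five half-lives take 16.7 to 20.8 days and the contraception period is 106.7 to 110.8 days.

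**The case against.** The strongest reply has four parts.

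1. **The wording sets a floor tied to a rule.** Criterion 6 says at least 5 days and offers five half-lives as an example; 8.2.5 brackets at least five half-lives. A careful reader who applies the rule to ~90 h reaches about 19 days. The multiplication was also right for its original input, so this is an outdated number and not a slip in calculation. All of that is true, but 5 is the only number of days either clause gives, and a participant agrees to a number of days.

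2. **The contraception effect is small.** No man is released with relevant drug present, and the protocol's risk table names no reproductive or genotoxic hazard that 14 fewer days would worsen. This stands, and it limits the point to a shortened margin.

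3. **Pregnancy collection is backed up elsewhere.** Appendix 4 reaches to about day 28 if participation is taken to end at follow-up. Abnormal outcomes count as SAEs (8.2.5), which are collected to follow-up (8.2.1), and 10.4.3 covers related SAEs from a post-study pregnancy that the investigator learns of. This reduces the practical gap considerably. However, the SAE routes catch only abnormal or serious outcomes, and Appendix 4 contradicts the 8.2.5 day count without correcting it. The 40% figure applies only to a site that follows that day count literally.

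4. **The pregnancy-test allowance says little about partners.** The SoA note "Follow up test may be obtained up to 37 days post last dose" concerns a test in participants, and other SoA tables restrict that test to women. It shows that participation-related checks can run past day 28, but it does not define how long partner pregnancies are collected. This also stands.

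**Conclusion.** The concern holds. In 5.1 criterion 6 and in 8.2.5, 5 days is equated with five terminal half-lives, which is true at 24 h and false at the ~90 h the protocol now reports. By the protocol's own rule the figures should be about 19 days for elimination, about 109 days in place of 95 for male contraception and sperm donation, and about 19 days in place of 5 for pregnancy collection.

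The protocol also leaves three candidate end points for pregnancy collection: 5 days (8.2.5 day count), about 19 days (8.2.5 rule) and about 28 days (Appendix 4 read with the follow-up visit).

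The result rests on the observed half-life of ~90 h, first-order elimination and the five-half-life rule the protocol itself chose. It does not depend on the exact half-life: no value in the assumed 80 to 100 h range brings five half-lives near 5 days. The point should be fixed but is not grave. It affects a safety margin and the consistency of safety reporting in a first-in-human study, and no endpoint, analysis or dose decision.

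**What to change.** - **5.1, criterion 6.** Replace 5 days with about 19 days, and state the total as about 109 days including the 90-day cycle.
- **8.2.5.** Replace 5 days with at least 19 days, or preferably tie the window to the follow-up visit about 28 days after the last dose. The second option agrees with Appendix 4 and still covers five half-lives for any half-life up to 28 x 24 / 5 = 134 h.
- **8.3 (optional).** Overdose monitoring continues until drug is no longer detectable, so its 5-day minimum does no harm, but raising it to about 19 days would keep the document consistent.
- **Consent form.** Align it if it carries the 5-day or 95-day figure. It was not available for review.

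The cost is about 14 more days of contraception for male participants. Pregnancy collection already reaches about day 28 under Appendix 4, so little is added there. Because criterion 6 is an eligibility criterion, the change needs ethics approval before implementation (10.1.1), and participants still in the study would be re-consented if the form changes (10.1.3). The sponsor should also decide whether to advise men already dosed who are still within the period. No analysis, power or sample size is affected.
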